7.3. Electrocardiogram/Echocardiogram

Overall interpretation of ECG data, including normal, abnormal and clinically significant, abnormal and not clinically significant will be summarized descriptively by the number and percentages of subjects at each visit, and the last assessment during the double-blind period.

A listing of all abnormal values for ECG will be provided.

Echocardiogram parameters (left ventricle ejection fraction and sphericity index) will be summarized descriptively, including change from baseline by visit, and the last assessment during the double-blind period. Overall interpretation of echocardiogram (normal, abnormal) will be summarized descriptively by the number and percentages of subjects at each visit, and the last assessment during the double-blind period.

7.4. Physical Examination

Physical examination results will be listed in subject listings only.

7.5. Vital Signs

Height, weight, and vital signs data will be summarized descriptively, including change from baseline at each post-baseline and the last assessment during double-blind period. A summary will also be provided by visit and overall of the number of subjects meeting criteria for hypertension based on age, gender, and height-adjusted systolic blood pressure and diastolic blood pressure percentile results [[Flynn 2017](#)].

- Normal BP: BP <90th percentile for age, sex, and height; or <120/<80 mm Hg for adolescents ≥ 13 years old;
- Elevated BP: BP reading ≥ 90 th percentile and <95th percentile for age, sex, and height; or 120 to 129/<80 mm Hg for adolescents ≥ 13 years old;
- Hypertension: BP ≥ 95 th percentile for age, sex, and height; or $\geq 130/80$ mm Hg for adolescents ≥ 13 years old.

8. CHANGES FROM THE PROTOCOL

The major changes to the planned analyses from the protocol are summarized as follows:

- NSAA total score will be calculated as the sum of the 16 scores (except for lifts head), instead of 17, based on Mayhew's publication [[Mayhew 2013a](#)].
- Aggregated odds ratio of NSAA will not be calculated because of the correlated information and possible inconsistent baseline within subjects. Due to the same reason, the aggregated odds ratio of PROM will not be calculated.
- Evaluable population defined in protocol is removed. The planned analysis using Evaluable population will be replaced by subjects with sufficient information in ITT, mITT, or as-treated population, where applicable.
- The protocol proposed comparison with external natural history cohorts will not be described in this SAP. This comparison will be described and performed in future if deemed necessary.

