9.4.5.3 North Star Ambulatory Assessment

The NSAA consists of 17 activities, each scored as 0, 1, or 2. The sum of these 17 scores will be used to form a total score. This total score will be analyzed using the ANCOVA analysis method outlined for the primary efficacy variable, for both the mITT and ITT populations, at the end of the double-blind and open-label phases. A separate analysis for the open-label phase will evaluate changes in total score in subjects with a baseline 6MWD ≥ 400 meters and < 7 years of age. Transformation of the total score to a linear scale [Mayhew 2013a] also will be performed. In addition, the odds of losing one or more of the NSAA items (score of 1 or 2 at baseline transitioning to a 0 score post-baseline) will be evaluated for ataluren versus placebo subjects using a risk ratio derived via re-sampling based analysis methods; the “lifts head” item will be excluded from this analysis because it does not fit the original construct of the NSAA based on Rasch analysis [Mayhew 2013a].

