6.2.3. North Star Ambulatory Assessment

The NSAA consists of 17 activities, each scored as 0, 1, or 2. The sum of 16 scores (except for lifts head) will be used to form a total score [Mayhew 2013a]. Hereafter, this NSAA total score will be referred as revised NSAA (rNSAA) total score. If an activity cannot be performed due to disease progression/loss of ambulation, a score of 0 will be assigned, and will not be considered as missing. If fewer than 13 of the 16 activities are performed, the total score will be considered missing. If from 13 to 16 activities are performed, the total score will be standardized by multiplying the sum of the scores in the x activities by 16/x.

The total score will be analyzed using the similar ANCOVA after MI model as 6MWD during the overall treatment period for ITT population. The estimated difference in the change from study baseline at Week 144 will be provided. The linear transformation of the total score [Mayhew 2013a] will be analyzed using the similar ANCOVA after MI model. The total score and linear score will also be summarized by visit during overall treatment period based on ITT population.

In addition, the number of subjects with loss of function of each NSAA items (score of 1 or 2 at baseline transitioning to a 0 score post-baseline) will also be summarized by treatment groups during overall treatment period for ITT population.

The change from baseline in rNSAA total scores and linear scores will be summarized by visit for subgroups below for ITT population:

- Region (North and Latin America, Europe, Asia Pacific)
- Stop codon (UAA, UAG, UGA)
- Baseline disease severity
 - Baseline 6MWD <300 meters
 - Baseline 6MWD \geq 300 meters to <400 meters
 - Baseline 6MWD \geq 400 meters

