2.3.2. Secondary Endpoints

The key secondary endpoints are:

- Slope of composite of average change in times to run/walk 10 meters, climb 4 stairs, and descend 4 stairs over 72 weeks
- Change from baseline to Week 72 in NSAA total score

Other secondary endpoints are:

- Change from baseline to Week 72 in 6MWD
- Composite of average change in times to run/walk 10 meters, climb 4 stairs, and descend 4 stairs at Week 72
- Change from baseline to Week 72 in time to run/walk 10 meters
- Change from baseline to Week 72 in time to climb 4 stairs
- Change from baseline to Week 72 in time to descend 4 stairs
- Time to loss of ambulation (LoA) over 72 weeks
- Time to loss of stair-climbing over 72 weeks
- Time to loss of stair-descending over 72 weeks
- Risk of loss of NSAA items over 72 weeks

- Ataluren safety profile characterized by type, frequency, severity, and relationship to study drug of any adverse events (AEs), or of abnormalities of laboratory tests, vital signs, physical examinations, or electrocardiograms (ECGs)

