6.2.2.3. North Star Ambulatory Assessment – Individual Items

The frequency of loss of function of each NSAA items (score of 1 or 2 at baseline transitioning to a 0 score post-baseline) will be tabulated by treatment group for both mITT and ITT populations.

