3.2.2.3. North Star Ambulatory Assessment – Individual Items

There is no change to the planned analyses for loss of function in individual items of North Star Ambulatory Assessment (NSAA) for ITT population.

3.2.2.4. *Loss of Ambulation (LoA) and Stair Climb/Stair Descend*

There is no change to the planned analyses for Loss of Ambulation (LoA) and Loss of Stair Climb/Stair Descend for ITT population.

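### Loss of NSAA items remains a secondary endpoint, but both SAPs replace the protocol's re-sampled risk ratio with per-item tables, so it has no effect estimate, confidence interval or test.

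*SAP*

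**What the plan says.** **Endpoint.** Double-blind SAP 2.3.2 lists "Risk of loss of NSAA items over 72 weeks" among its other secondary endpoints, as Protocol 2.2.1.2 does. Protocol 2.2.2.1 and open-label SAP 2.3.2 carry the 144-week counterpart.

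**Protocol analysis.** Section 9.4.5.3 takes as outcome "the odds of losing one or more of the NSAA items", where a loss is an item scored 1 or 2 at baseline that falls to 0 afterwards. The outcome "will be evaluated for ataluren versus placebo subjects using a risk ratio derived via re-sampling based analysis methods". The item on lifting the head is left out, so 16 of the 17 items count.

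**Double-blind SAP.** Under 6.2.2.3 the frequency of loss of each item "will be tabulated by treatment group for both mITT and ITT populations". Section 8 gives the reason for going no further: "Aggregated odds ratio of NSAA will not be calculated because of the correlated information and possible inconsistent baseline within subjects". The same bullet drops the corresponding ratio for the upper limb PROM.

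**Open-label SAP.** Under 6.2.3 the per-item counts "will also be summarized by treatment groups during overall treatment period for ITT population". Its Section 8 list of changes does not mention the dropped ratio.

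**Changes-from-planned-analysis document.** Section 3.2.2.3 restores nothing: "There is no change to the planned analyses for loss of function in individual items".

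**The concern.** A named secondary endpoint has lost its treatment comparison. The other efficacy endpoints in double-blind SAP 2.3.2 each keep a between-arm analysis: mixed models or ANCOVA for 6MWD, the timed tests and the NSAA total, and log-rank with Cox models for loss of ambulation and stairs. Item loss alone ends as a set of tables.

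The reasons in Section 8 are also aimed at something other than what the protocol planned. They reject an aggregated odds ratio. The protocol mentions odds but specifies a risk ratio by re-sampling, and the SAP does not say why that method would fail.

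At stake is an interpretable result. A reader with up to 16 item rows per arm has no summary of the effect and no measure of its uncertainty, and the obvious shortcut of adding up the rows is statistically invalid.

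**Working it through.** **1. The plan's own figures.** The documents give no loss rate, within-boy correlation or power for item loss. The only power calculation (double-blind SAP 2.4) is for the 6MWD slope, and it reproduces: n per arm = 2 × (1.960 + 1.036)² × 2.058² / 1.0² = 76.1, rounded up to 77, so 154 in all. Inflation for 5% dropout gives 154 × 1.05 = 161.7, stated as 162, or 81 per arm. The ITT set is stated as 359, or about 180 per arm. These sizes are used below. All item-loss inputs are assumptions.

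**2. First reason: correlated items.** On the protocol's wording, read per boy, the outcome is one yes/no value per boy, so correlation between items within a boy does not arise. For a ratio of items lost to items at risk, correlation matters only if the variance ignores it. Null simulations used 81 or 180 boys per arm, 8–16 at-risk items per boy, 10–20% loss per item, within-boy ICC 0.1–0.5 and 1,500 trials per setting (Monte Carlo standard error √(0.05 × 0.95 / 1500) = 0.6 points):

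| Analysis | Type I error, nominal 5% |
|---|---|
| Items pooled as independent | 17.5–44% |
| Items lost / at risk, re-sampling whole boys | 4.1–6.0% |
| Per boy, lost one or more items | 4.3–6.6% |

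**3. Second reason: inconsistent baseline within subjects.** This could mean items already at 0, or items starting at 1 rather than 2. The first kind cannot be lost, and the protocol's definition already removes them from the at-risk set. For the second kind, items starting at 1 were given a 25% loss risk and items starting at 2 a 7% risk, with a mix that varied by boy. Naive pooling rejected in 20–36% of trials, re-sampling by boy in 4.5–6.0%.

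**4. Unit of re-sampling.** The protocol does not name it. Brothers are assigned the same arm (double-blind SAP 6.1.3.7). With an assumed 10–20% of boys in brother pairs with fully shared risk, type I error was 5.7–8.4% re-sampling boys and 4.7–6.7% re-sampling families. Family is the safer unit.

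**5. Power.** For the share of at-risk items lost, 81 per arm, 8–16 items, boy-clustered variance, ICC from 0.05 to 0.30:

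| Placebo loss per item | Item risk ratio | Power |
|---|---|---|
| 25% | 0.70 | 90% down to about 49% |
| 10% | 0.70 | 49% down to 21% |
| 25% | 0.85 | 35% down to 14% |

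For losing one or more items, with item risk ratio 0.70 and ICC 0.1–0.5, power at 81 per arm was 21–32% at 10% loss and 34–44% at 20% loss. At 180 per arm it was 36–66% and 60–80%.

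The per-boy outcome can approach a ceiling. With 12 independent items, 1 − 0.75¹² = 97% of placebo boys would lose at least one, against 1 − 0.825¹² = 90% at item risk ratio 0.70, a per-boy ratio of only 0.93. At 10% loss the figures are 1 − 0.90¹² = 72% and 1 − 0.93¹² = 58%, ratio 0.81. Correlation lowers these proportions. This is the case for adding the share of items lost as a supporting measure.

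For comparison, one item row tested alone (25% versus 17.5%, 75% of boys at risk) has effect size h = 2·asin√0.25 − 2·asin√0.175 = 0.184. Power is Φ(0.184 × √(60.75/2) − 1.96) = 17% at 81 per arm.

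**The case against.** The strongest case against is that this is small and disclosed. The double-blind change is stated with reasons. Version 1.0 of that SAP is dated 04APR2022, before the first lock on 11April2022. The endpoint sits outside the fixed test sequence, and the NSAA is formally compared through its total score, the second key secondary endpoint. All of this stands and limits the weight of the point.

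A late repair also has a cost. Double-blind results are already reported in the changes document, so choosing a measure, time frame and re-sampling unit now is a decision made after unblinding. That stands too. Keeping to the protocol's own outcome narrows the choice, and the timing must be stated.

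A reader might infer more than the documents support:
- *That the arms are never compared.* The tables are by treatment group, so the arms can be compared by eye. What is missing is an estimate with its uncertainty.
- *That the comparison was dropped after seeing results.* The dates show otherwise for the double-blind SAP.
- *That the protocol already re-samples by boy.* It names no unit.
- *That the plan carries an inflated error rate.* The 18–44% belongs to pooling items as independent, which no document plans and which Section 8 in effect declines.
- *That a sensitive analysis was discarded.* The 90% power figure is the most favourable scenario; others fall well below 50%.

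**Conclusion.** The point holds as a gap in analysis. The endpoint is declared in the protocol and both SAPs, the protocol planned a between-arm risk ratio, and both SAPs stop at tables. The two reasons given rule out a naive pooled ratio only. The open-label SAP also leaves the change unlisted.

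The validity conclusion rests on simulation under assumed loss rates and correlations, but was stable across them: near 5% for re-sampling by boy or family and for the per-boy outcome, with a modest excess when boys are re-sampled and brothers share risk. No claim can be made that the comparison would be well powered. The 14–90% range covers only the three scenarios shown and the share of at-risk items lost; 10% loss combined with a risk ratio of 0.85 would fall lower still. The change is worth making because it is cheap and completes a declared endpoint. It does not affect the primary conclusion or alpha control.

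**What to change.** In double-blind SAP 6.2.2.3 and open-label SAP 6.2.3:
- Add a risk ratio with 95% CI for the protocol's outcome: loss of one or more of the 16 items (lifting the head excluded), from 1 or 2 at baseline to 0 post-baseline. Compare ataluren with placebo over 72 weeks, and early with delayed start over 144 weeks, because both arms receive ataluren after Week 72.
- Obtain the interval by re-sampling families within arm.
- State whether a single 0 at any visit counts as a loss, and how missing post-baseline scores and early dropouts are handled. Double-blind SAP 6.2.1.2 already scores an activity 0 when progression prevents it; say whether that applies here.
- The share of at-risk items lost may be reported as a supporting measure.
- Keep the item tables as description.

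Amend the NSAA part of the bullet in double-blind SAP Section 8 and keep its PROM disclosure. List any remaining departure in open-label SAP Section 8. Label the result nominal and outside the fixed sequence and, for the double-blind period, specified in the protocol but reinstated after the first database lock.

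The cost is SAP wording and a short program, with no new data and no alpha. The downside is one more estimate without multiplicity control. If the sponsor prefers not to add it, the endpoint should be relabelled descriptive in both SAPs and the change listed.

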10. TABLES, GRAPHS, AND LISTINGS SHELLS

The tables, listings, and graphs shells for the study will be provided in a separate document.

APPENDIX 1. SCHEDULE OF ASSESSMENTS

| Study Period | Screening | Double-Blind Treatment | | | | | | | | Notes |
|---|-----------|------------------------|----|-----|-----|-----|-----|-----|---|--|
| Study Week | -2 weeks | 1 | 12 | 24 | 36 | 48 | 60 | 72 | 2-week screening period may be extended by 1 week if necessary to schedule pretreatment MRI | |
| Study Day | | 1 | 84 | 168 | 252 | 336 | 420 | 504 | | |
| Visit Window (days) | | | ±7 | ±7 | ±7 | ±7 | ±7 | ±7 | | |
| Visit Number | 1 | 2 | 3 | 4 | 5 | 6 | 7 | 8 | At Visit 2, complete assessments before first dose | |
| Visit Day | | 1 | 2 | | | | | 1 | 2 | 2-day visits only at Visit 2 and Visit 8 |
| Informed consent | X | | | | | | | | | May be obtained prior to Visit 1 (eg, by phone) |
| Enter subject in IRT system | X | | | | | | | | | Access IRT system to enter subject |
| Clinical and medication history | X | | | | | | | | | |
| Hepatitis screen | X | | | | | | | | | |
| Urinalysis sample | X | X | | X | | X | | X | | |
| EQ-5D and DMDSAT | X | X | | X | X | X | X | X | | Provided to subject at Visit 1 for at-home completion between visits and reviewed for compliance in clinic |
| DMD Upper Limb PROM | | X | | X | X | X | X | X | | Performed only in subjects ≥7 years at baseline |
| Height | X | X | | X | X | X | X | X | | |
| Weight | X | X | | X | X | X | X | X | | |
| Physical examination | X | X | | X | | X | | X | | Full (Visit 1, 8) or symptom-directed (Visit 2, 4, 6) |
| Concomitant medications | X | X | | X | X | X | X | X | | |
| Adverse events | X | X | | X | X | X | X | X | | |
| Genotyping sample | | X | | | | | | | | |
| Hematology sample | X | X | | X | | X | | X | | |
| Biochemistry sample | X | X | | X | | X | | X | | To be collected in fasted state (except Visit 1) |
| Vital signs | X | X | | X | X | X | X | X | | |
| Myometry | X | X | | X | X | X | X | X | | Performed only in subjects <7 years at baseline |
| PUL | X | X | | X | X | X | X | X | | Performed only in subjects ≥7 years at baseline |
| 6-minute walk test (1 st test) | X | X | | X | X | X | X | X | | |
| 6-minute walk test (2 nd test) | | | X | | | | | | X | |
| NSAA | X | X | | X | X | X | X | X | | |
| Timed function tests | X | X | | X | X | X | X | X | | |
| Study drug dispensed | | | X | X | X | X | X | X | X | Open-label study drug dispensed at Visit 8 |
| Study drug compliance | | | | X | X | X | X | X | | |
| 12-lead ECG | X | | | X | | X | | X | | |
| Spirometry | X | X | | | | | | X | | Required at all visits after subject loses ambulation |
| Echocardiogram | X | | | | | | | X | | |

| Study Period | Screening | Double-Blind Treatment | | | | | | | | Notes |
|---------------------|-----------|------------------------|----|-----|-----|-----|-----|-----|---|---|
| Study Week | -2 weeks | 1 | 12 | 24 | 36 | 48 | 60 | 72 | 2-week screening period may be extended by 1 week if necessary to schedule pretreatment MRI | |
| Study Day | | 1 | 84 | 168 | 252 | 336 | 420 | 504 | | |
| Visit Window (days) | | | ±7 | ±7 | ±7 | ±7 | ±7 | ±7 | | |
| Visit Number | 1 | 2 | 3 | 4 | 5 | 6 | 7 | 8 | At Visit 2, complete assessments before first dose | |
| Visit Day | | 1 | 2 | | | | | 1 | 2 | 2-day visits only at Visit 2 and Visit 8 |
| Randomization | | | X | | | | | | | Access IRT system to randomize subject |
| Upper leg imaging | | X | | X | | X | | X | | Performed only at pre-qualified sites. May be done between Visits 1 and 2 (pre-treatment assessment) or ±4 weeks of visit (post-treatment assessments). |

Abbreviations: DMD, Duchenne Muscular Dystrophy; DMDSAT, DMD Functional Ability Self-Assessment Tool; ECG, electrocardiogram; EQ-5D, EuroQoL 5-Dimension; IRT, interactive response technology; NSAA, North Star Ambulatory Assessment; PROM, Patient-Reported Outcome Measure; PUL, Performance of Upper Limb

APPENDIX 2. SAMPLE SAS PROGRAM FOR THE PRIMARY ANALYSIS FOR PRIMARY ENDPOINT USING ANCOVA MODEL

The analysis will employ of the following SAS procedures:

- For each analysis population or identified population for analysis, perform the MI for the population once. The MI results will be used for all analyses planned for the population.
- 100 datasets will be generated where missing data at intermediate visits will be imputed for each treatment group using non-missing data from all subjects within the treatment group by a Monte Carlo Markov Chain (MCMC) imputation model using the MCMC statement in the SAS PROC MI procedure. As a result, each dataset will only have missing ending data, or a monotone missing data pattern.
- For each dataset from the prior step, missing ending data will be imputed by a regression imputation model using the SAS PROC MI procedure with the REGRESSION option in the MONOTONE statement using the CCMV assuming that the missing values are MNAR. The regression imputation model includes an intercept and the slopes of the measurements from all previous visits for the imputation of subsequent visits.
- The resulting complete datasets from the prior step will be processed via a SAS DATA step to create change from baseline values for each treatment group at each visit.
- The resulting datasets will be analyzed using SAS PROC MIXED to perform the analysis of covariance for the primary efficacy endpoint by study visit.
- The SAS PROC MIANALYZE procedure will be used to combine the LS mean and treatment versus placebo difference estimates to produce the final analysis results.

Sample SAS code corresponding to the above steps appears below:

```
/******  
Multiple imputation assuming MNAR using complete case missing value pattern  
  
TRTn: Treatment (0=Placebo, 1=Ataluren)  
Cortico: Steriod use at randomization  
C6mwd: Baseline 6MWD categories  
mITTfl: Identifier for mITT population  
*****/  
  
* 1st: Generate 100 datasets to impute missing interim data by treatment  
group using MCMC option;  
proc sort data=smwt; by trtn usubjid; run;  
proc MI data=smwt out=smwt_mono minimum=0 nimpute=100 minmaxiter=5000  
seed=93182;  
  WHERE mITTfl="Y";  
  BY trtn;  
  VAR SmwdWKBL SmwdWK12 SmwdWK24 SmwdWK36 SmwdWK48 SmwdWK60 SmwdWK72;  
  MCMC chain=multiple impute=monotone;  
run;
```

* 2nd: Impute missing ending data using monotone statement with regression option and assuming MNAR using CCMV;

```
proc sort data=smwt_mono out=smwt_mono; by _imputation_ trtn usubjid; run;
proc MI data=smwt_mono out=smwt_ccmv minimum=0 nimpute=1 minmaxiter=5000
seed=93035;
  WHERE mITTfl="Y";
  BY _imputation_ trtn;
  VAR SmwdWKBL SmwdWK12 SmwdWK24 SmwdWK36 SmwdWK48 SmwdWK60 SmwdWK72;
  MONOTONE reg(/details);
  MNAR Model (SmwdWK12 SmwdWK24 SmwdWK36 SmwdWK48 SmwdWK60
SmwdWK72/Modelobs=CCMV);
run;
```

* 3rd: Create datasets for ANCOVA;

```
data smwt_reg;
  set smwt_ccmv;
  AWeek= 0; Avalimp=SmwdWK0; CFBimp=SmwdWK0-BL6mwd; output;
  AWeek=12; Avalimp=SmwdWK12; CFBimp=SmwdWK12-BL6mwd; output;
  AWeek=24; Avalimp=SmwdWK24; CFBimp=SmwdWK24-BL6mwd; output;
  AWeek=36; Avalimp=SmwdWK36; CFBimp=SmwdWK36-BL6mwd; output;
  AWeek=48; Avalimp=SmwdWK48; CFBimp=SmwdWK48-BL6mwd; output;
  AWeek=60; Avalimp=SmwdWK60; CFBimp=SmwdWK60-BL6mwd; output;
  AWeek=72; Avalimp=SmwdWK72; CFBimp=SmwdWK72-BL6mwd; output;
run;
```

...

* 4th: Conduct ANCOVA analysis on imputed datasets;

```
proc sort data=adsmwdimp out=adsmwdimp; by _imputation_; run;
ods exclude all;
proc mixed data=adsmwdimp method=REML;
  WHERE mITTfl="Y" and Aweek=72;
  BY _imputation_;
  CLASS Cortico Trtn C6mwd;
  MODEL CFBimp=BL6MWD Trtn Cortico C6MWD / CL;
  LSMEANS Trtn/ diff=control('0') cl alpha=0.05;
  ods output diffs=diff_mi lsmeans=lsn_mi;
run;
ods exclude none;
```

* 5th: Use Proc MIAnalyze to obtain final analyiss results;

* LS Means;

```
proc mianalyze parms(classvar=full)=lsn_mi;
  CLASS Trtn;
  MODELEFFECTS Trtn;
  ods output parameterestimates=lsn_out;
run;
```

* Treatment differences;

```
proc mianalyze parms(classvar=full)=diff_mi;
  CLASS Trtn;
  MODELEFFECTS Trtn;
  ods output parameterestimates=diff_out;
run;
```

The table below lists the random seeds to be used for the primary and secondary analyses and some additional seeds should they be required. The random seeds were created using SAS uniform generator RAND("Uniform") with a seed of 20210126.

| Endpoint/Analysis | Seed for Step 1 (impute missing interim data) | seed for Step 2 (impute missing ending data) |
|--|---|--|
| 6MWD (mITT, Section 6.1.2) | 93182 | 93035 |
| 6MWD (ITT, Section 6.1.3.2) | 31096 | 27324 |
| 6MWD (PP, Section 6.1.3.2) | 96919 | 60747 |
| 6MWD (Covid19 impact, mITT, Section 6.1.3.6) | 57237 | 96213 |
| 6MWD (Covid19 impact, ITT, Section 6.1.3.6) | 81564 | 23187 |
| NSAA (mITT, Section 6.2.1.2) | 53056 | 44931 |
| NSAA (ITT, Section 6.2.1.2) | 78128 | 55295 |
| 10 Meter Run/Walk (mITT, Section 6.2.2.2) | 14792 | 5438 |
| 10 Meter Run/Walk (ITT, Section 6.2.2.2) | 93543 | 15827 |
| 10 Meter Run/Walk (baseline 6MWD <300 meters, Section 6.2.2.2) | 64644 | 67275 |
| 4-stair climb (mITT, Section 6.2.2.2) | 40100 | 14015 |
| 4-stair climb (ITT, Section 6.2.2.2) | 75269 | 1604 |
| 4-stair descent (mITT, Section 6.2.2.2) | 13807 | 67037 |
| 4-stair descent (ITT, Section 6.2.2.2) | 69749 | 60769 |
| PUL (mITT, Section 6.3.1) | 20889 | 68149 |
| PUL (ITT, Section 6.3.1) | 53584 | 22 |
| DMD Upper Limb PROM (mITT, Section 6.3.1) | 57087 | 56786 |
| DMD Upper Limb PROM (ITT, Section 6.3.1) | 37430 | 59741 |
| Myometry (ITT, Section 6.3.2) | 75789 | 20780 |
| If additional analyses need to be performed, seeds below will be used | | |
| Additional Analysis #1 | 47997 | 55087 |
| Additional Analysis #2 | 12688 | 70229 |
| Additional Analysis #3 | 91077 | 10733 |
| Additional Analysis #4 | 28506 | 17466 |
| Additional Analysis #5 | 17445 | 33103 |

APPENDIX 3. SAMPLE SAS PROGRAM FOR THE SENSITIVITY ANALYSIS OF CHECKING THE ASSUMPTION OF MISSING AT RANDOM

As sensitivity analysis of checking the assumption of MAR described in Section 6.1.3.4 will use following steps:

1. Keep all placebo subjects who completed the double-blind treatment period, and the subjects who identified prior to database lock
2. Similar to step 1 in [Appendix 2](#), generating 100 datasets to impute interim data without considering the treatment
3. Similar to step 2 in [Appendix 2](#), impute the missing ending data using monotone statement
4. Merge the imputed information for the identified subjects back to original dataset
5. Perform MMRM analysis
6. Use Proc MIAnalyze to obtain final results

Rand seed used for this multiple imputation are shown below.

| Endpoint/Analysis | Seed for Step 1 (impute missing interim data) | seed for Step 2 (impute missing ending data) |
|---|---|--|
| 6MWD for checking MAR assumption (mITT) | 49564 | 50402 |

